1.2 Potential Risks and Benefits

1.2.1 Known Potential Risks

1.2.1.1 Known Potential Risks of DMEK

The risks and discomforts for patients undergoing DMEK are the same regardless of study participation. Potential risks of DMEK include:

- mild pain for approximately one week after surgery
- temporary discomfort from the eye examination or eye drops, which may include stinging, itching, or redness
- serious infection or bleeding in 1 in 1,000 patients and serious problems related to anesthesia in 1 in 10,000
- in rare instances topical drops used during standard of care exams can cause an allergic reaction, seizures, and an irregular heartbeat
- development of a rapid rise in the eye pressure
- development of glaucoma

- additional surgery required due to healing problems or movement out of position of the donor cornea
- retinal swelling or detachment
- loss of vision
- rejection reactions occur approximately in about 2-3% of eyes within 5 years of surgery,⁴⁵ but are usually reversible if treated promptly with topical corticosteroids, but sometimes it leads to failure of the transplant
- endophthalmitis: a serious intraocular infection that requires prompt treatment and may cause permanent loss of vision or in severe circumstances loss of the eye
- corneal infection: a serious microbial infection of the cornea that requires immediate treatment and may result in permanent scarring and possible permanent loss of vision requiring a repeat of the corneal transplant
- rare chance of dissemination of a communicable disease from the donor tissue
- corneal scarring: permanent haze or cloudiness in the cornea that may result in permanent loss of vision and/or requiring a repeat of the corneal transplant
- corneal neovascularization: blood vessel growth into the cornea that could subject the transplant to a higher risk for rejection and/or permanent loss of vision, requiring a repeat of the corneal transplant
- corneal swelling: thickening of the cornea that may result in loss of vision which may or may not be reversible. If not reversible, another corneal transplant may be required to restore the vision
- wrinkling of the corneal layers: wrinkling of the donor cornea as it heals may result in blurred vision and require another corneal transplant

1.2.1.2 Known Potential Risks of Study Participation

The following are risks of procedures that are not necessarily part of routine care but are being performed for the purposes of this study:

- Fingerstick blood collection: Transient mild discomfort common. In about 1 in 10 times a small amount of bleeding under the skin will produce a bruise. A small scar may persist for several weeks. The risk of an infection is less than 1 in 1000.
- Subjects will be informed of their HbA1C results. Some who have not been previously diagnosed with diabetes might be uncomfortable to learn that their HbA1C level suggests that they may have diabetes. Similarly, those that already know they have diabetes might be uncomfortable to learn that their HbA1C level suggests their diabetes is not under good control.
- There are no known risks to the imaging procedures.

1.2.2 Known Potential Benefits

Study participants may not benefit directly from participation in this study. If the study identifies certain donor corneas as being associated with worse outcomes, eye banking practice could formally change to discourage use of potentially inferior tissue. In the future, if a study participant requires another DMEK in either the same eye or their other eye, the information obtained from this study might benefit them.

1.2.3 Risk Assessment

The risks for events noted in Section 1.2.1.1 are no greater when participating in the study compared with standard care. The likelihood of receiving a cornea from a donor with diabetes in this study will be the same or less compared to the manner in which corneal tissue is distributed nationally (see section 1:1). Other than the study procedures of allocation and distribution of donor tissue in a masked manner, finger stick blood collection and non-contact corneal photographs, the study procedures include collection of data from standard of care office visits, surgical techniques and post-operative care and evaluations.

1.3 General Considerations

The study is being conducted in compliance with the policies described in the study policies document, with the ethical principles that have their origin in the Declaration of Helsinki, with the protocol described herein, and with the standards of Good Clinical Practice (GCP).

When feasible, data will be directly collected in electronic case report forms, which will be considered the source data.

Chapter 2: Study Enrollment and Participant Screening

2.1 Participant Recruitment and Enrollment

Note: throughout this document the term randomization may be used in reference to the study's assignment of donor tissue. However, the process is actually a minimization procedure as explained in Section 3.2.2 rather than traditional randomization; nonetheless for simplicity we retain the term randomization for descriptive purposes.

The goal is to randomize 1420 study eyes with at least 1278 study eyes followed with complete outcome assessments. Participants who have signed consent and started the screening process may be permitted to continue into the trial, if eligible, even if the randomization goal has been reached. Up to 2000 individuals may be enrolled (i.e., sign informed consent) to enable randomization of the 1420 study eyes.

Study participants will be enrolled at ~30 clinical centers in the US. All eligible participants will be included without regard to gender, race, or ethnicity. There is a restriction of a maximum of 20% of the number of eyes (284 eyes) to be randomized by a single surgeon toward the overall recruitment goal.

2.1.1 Informed Consent and Authorization Procedures

Potential eligibility may be assessed as part of a routine-care examination. Before completing any procedures or collecting any data that are not part of usual care, informed consent will be obtained. The informed consent process is described in Section 10.3.

The study will be discussed with the potential study participant by study staff. If the potential participant lacks the capacity to consent, then they should not be approached to consent for the study. The sites' policies and procedures shall be followed to determine capacity, and in general, if the person was able to consent for the transplant themselves, then they can consent for the study themselves. If they require a legally authorized representative to consent to the transplant on their behalf, then they should not be approached to participate in the study.

The potential study participant will be provided with the Informed Consent Form to read in a language understandable to the participant (in English or Spanish as applicable) and will be given the opportunity to ask questions. Potential study participants will be encouraged to discuss the study with family members and their personal physicians(s) before deciding whether to participate in the study. If the potential study participant is interested in the study, the paper Informed Consent Form will be signed by both the participant and an authorized study designee. The subject will be given a signed copy by the study team for their records.

As part of the informed consent process, each participant will be asked to sign an authorization for release of personal information, which may be within the consent form or a separate form. The investigator, or his or her designee, will review with the potential participant the study-specific information that will be collected and to whom that information will be disclosed. After speaking with the participant, questions will be answered about the details regarding authorization.

A participant is considered enrolled when the informed consent form has been fully executed and HIPAA authorization has been provided.

2.2 Participant Inclusion Criteria

Individuals must meet all of the following participant-level inclusion criteria and have at least one eye meeting the study eye inclusion criteria in order to be eligible to participate in the study.

2.2.1 Study Participant-level Criteria

1. Age range 30-<91 years with minimum life expectancy of at least 1 year.
2. Willingness to return to study site for follow up at 1 month and 1 year.
3. Fluent in English or Spanish.
4. Willingness to have fingerstick blood sample collected to determine HbA1c level at entry and 1 year.
 - a. The participant must agree to have their primary care provider contacted (or an appropriate referral provided) if they were not known to have diabetes and the HbA1c suggests they may have diabetes. Similarly, if already known to have diabetes and the HbA1c is high, the participant must agree to have their primary care provider contacted or an appropriate referral provided.

2.2.2 Study Eye Criteria

1. At least one eye clinically recommended for DMEK that is able to be scheduled for DMEK between 5 and 90 days after enrollment.
2. If second eye is enrolled, must be scheduled for DMEK between 7 days and 6 months after DMEK on the first eye.
3. Presence of a condition related to endothelial dysfunction which will be treated by DMEK.

Eligible indications for DMEK include:

- a. Presence of FECD meeting at least one of the following:
 - i. Phakic FECD with or without cataract
 1. Triple procedure including DMEK for FECD, cataract extraction and posterior chamber intraocular lens implantation (IOL) is allowed
 - ii. Pseudophakic FECD with posterior capsule supported, sulcus supported, or scleral-fixated posterior chamber IOL
- b. Pseudophakic corneal edema with posterior capsule supported, sulcus supported, or scleral-fixated posterior chamber IOL without FECD
- c. Failed DSAEK or DMEK originally performed for the same indications above without current exclusion criteria below, as described below.

NOTES:

- *Stromal vascularization is acceptable, as long as not visually significant (by investigator's judgement)*

- *Penetrating keratoplasty and DSAEK will not be included procedures; only DMEK*

2.3 Participant Exclusion Criteria

Individuals meeting any of the following exclusion criteria at baseline will be excluded from study participation.

1. Pregnant or planning to become pregnant prior to the DMEK study surgery, based on verbal report.
2. Lack cognitive capacity such that consent could not be provided. Such individuals are excluded because they are at greater risk for post-operative complications if they do not follow proper instructions (use of drops, ocular protection, physical positioning) and therefore can confound study outcomes.
3. Presence of a condition that has a high probability for failure (e.g., failed penetrating keratoplasty, uncontrolled uveitis)
4. Stromal vascularization that will impede assessment of recipient stroma clarity
5. Other primary endothelial dysfunction conditions including posterior polymorphous corneal dystrophy and congenital hereditary corneal dystrophy
6. Indication for surgery that is not suitable for DMEK (e.g, keratoconus, stromal dystrophies and scars)
7. Aphakic corneal edema with or without FECD
8. Anterior chamber IOL in study eye prior to DMEK or planned placement of anterior chamber IOL during DMEK
9. Presence of vitreous in the anterior chamber
10. Planned IOL exchange of an anterior chamber IOL with a posterior chamber IOL in study eye at time of study DMEK
11. Pre-operative central sub-epithelial or stromal scarring that could impact post-operative recipient stromal clarity assessment
12. Presence of anterior synechiae
13. Peripheral anterior synechiae in the angle greater than a total of three clock hours
14. Uncontrolled glaucoma with or without prior filtering surgery, tube shunt placement, or MIGS. *Uncontrolled glaucoma is defined as intraocular pressure > 25mm Hg.*
15. Controlled glaucoma with prior tube shunt placement for glaucoma (*controlled glaucoma with MIGS or trabeculectomy is allowed*)
16. Fellow eye visual acuity < 20/200 due to an ocular condition other than cornea disease that would be a candidate for DMEK
17. IOP <8 mmHg
18. Topical Rho kinase inhibitor, including Rhopressa, used within 1 month prior to study entry and anticipated during the course of the study
19. Fellow eye enrolled in the DEKS that has met study criteria for graft failure.

Study eye eligibility is determined at the time DMEK surgery is scheduled. A participant can contribute two study eyes if both eyes are eligible. The eligibility of the second eye, if applicable, will be assessed at the time surgery on the second eye is scheduled; second eye surgery as part of the study can be performed between 7 days and 6 months (182 days) after DMEK on the first eye. If participant agrees to second eye study participation, he/she will not receive a cornea from a donor with known diabetes in both study eyes. Specifically, if the first eye received a cornea from a donor with known diabetes, after thorough medical record review as part of standard eye banking practices (see Section 3.2.2), the second eye will receive a cornea from a donor without known diabetes. (Study surgery could thus potentially be cancelled if a donor cornea without known diabetes is not available). If the first eye received a cornea from a donor without known diabetes, the second eye will proceed through the minimization algorithm for assignment of donor tissue. Note, because of the reclassification process based on HbA1c testing at the central laboratory, this means that donors not known to have diabetes after thorough eye bank staff medical record review, may still have diabetes that was not known at the time of the keratoplasty procedure. This testing is not standard practice and could delay proceeding with the keratoplasty if the cornea could not be placed until the result (HbA1c value < or \geq 6.5%) was returned. Therefore, there is a possibility that a participant who agreed to both eyes participating in the study can in both eyes receive a cornea from a donor classified as having diabetes based upon post-mortem study-specific HbA1c laboratory values (\geq 6.5%) that are not acquired in standard practice.

2.4 Screening/Pre-operative Procedures

After informed consent has been signed, a potential participant will be evaluated for study eligibility through the elicitation of a medical history and a routine examination including a dilated eye examination. There are no examination procedures required to assess patient eligibility other than those that are part of standard patient care. Historical data (which may predate the date of informed consent) may be obtained from the medical record after informed consent has been signed to acquire baseline data described below.

2.4.1 Data Collection and Testing

The following procedures/data will be performed/document for each study eye, unless otherwise specified:

- Inclusion and exclusion criteria assessed
- Demographics (date of birth, sex, race and ethnicity)
- Contact information (site enters into limited access study database)
- Medical history (including history and complications of diabetes, last HbA1c, and any ocular treatments for diabetes)
- Current diabetic and selected systemic and topical ocular medications
- Slit lamp examination (including FECD grading, assessment of other corneal dystrophies, presence of corneal vessels, presence of corneal opacities, anterior synechiae and lens status)
- Intraocular pressure

- Dilated fundus exam for grading of diabetic retinopathy

Once participant eligibility has been confirmed and informed consent has been obtained, a fingerstick blood sample will be collected for HbA1c determination prior to or within about 1 month of surgery. A fingerstick blood sample for HbA1c determination will be collected at the 12-month follow-up visit as well to monitor diabetes control and also to detect new diabetes in the original non-diabetic group.

Screening procedures will last approximately 1 hour.

- Those participants that were unaware they had diabetes will be reclassified as diabetic for study purposes based on this measurement. See Clinical Site Manual of Procedures for details regarding dissemination of participant HbA1c results.

2.5 Screen Failures

Individuals who do not initially meet study eligibility requirements may be rescreened at a later date per investigator discretion.

Chapter 3: Donor Eligibility and Cornea Assignment, Eye Banks

3.1 Eye Bank Procedures

Eye bank procedures will mimic standard procedures as closely as possible to minimize disruption to their normal routine, with the exception of procedures related to donor assignment including classification of donor diabetes status and specular microscopy (including calibration, technician certification, and procedure for obtaining specular images). Eye banks will be able to use any FDA-approved hypothermic (2-8°C) storage solution for intermediate term storage.

3.2 Donor Information, Procurement of Tissue and Other Samples

1. Donor information will be obtained by the eye bank's usual routine.

The eye banks must have authorization for research use in order to obtain a blood sample and skin tissue biopsy for the study. The eye banks may need to add a statement to their usual authorization forms referencing the DEKS to assure that they have proper authorization to take blood and skin biopsy samples for the purpose of the study. The Coordinating Center (CC) will work with each eye bank and provide templates for authorization for research.

2. Eye banks will follow their usual routine for procurement of tissue.

In addition to the usual cornea tissue procurement, the eye banks will also need to draw/obtain a whole blood sample from the potential donor for cadaveric HbA1c testing. If there is proper authorization for skin biopsies referred to above, the eye bank should also obtain a skin tissue sample for AGE testing at the time of recovery. See specific DEKS Eye Bank Procedures Manual, Advanced Research and Diagnostics Laboratory (ARDL) Eye Bank Central Laboratory Manual of Procedures, and the AGE Testing Program and Procedure Manual for details.

3.2.1 Donor Cornea Tissue Suitability

1. All eye banks will follow their procedural routine for procurement of cornea tissue and determination of suitability for DMEK in accordance with the Medical Standards and Procedure Manual of the EBAA. This includes standard serologic testing, specular microscopy, and slit lamp examination.

2. The following eligibility criteria will apply to all donor cornea tissue assigned to study eyes.

- Must meet current EBAA standards for human corneal transplantation
- Age of donor at time of death 50–75 years
- If the donor body was refrigerated or eyes on ice within 12 hours of death, the body or eye may stay refrigerated up to 24 hrs; if no refrigeration then the death to preservation time should be <12 hrs
- Preservation time ≤ 11 days
- Eye bank determined minimum ECD (at screening) of ≥ 2300 cells/mm²
- Pleomorphism/Polymegethism: At eye bank and medical director discretion

- Guttae: no true guttae present
- No evidence of central endothelial cell damage/trauma or dystrophy, such as FECD, by slit lamp examination

3.2.2 Determining Diabetic Status

Eye Banks should review various data collection documents and consult with treating physicians to help collect information to confirm diabetes status. If there are conflicting data found within the various data collection documents, continue to request additional primary care records, consults, and other sources of electronic health records as available. Examples include, as available:

- DRAI – Donor Risk Assessment Interview⁴⁶ – the current uniform DRAI for tissue banks has the following question: Did he/she EVER have diabetes? If yes a) for how many years? b) Was it treated? If yes How? The eye banks should add this question to the “eye only” DRAI to obtain diabetes information in addition to medical information. Eye Banks should also obtain the name of the treating physician in order to perform a follow up consult.
- Hospital medical record
- Physician consults
- Primary Care/Internist Medical Records

Defining Diabetic Status

For the purpose of tissue assignment for the minimization procedure, the eye bank will define the donor as having diabetes using ICD-10 codes and medical records with respect to diagnoses and treatments. Refer to the Eye Bank Manual of Procedures for detailed definitions.

Only donors definitely diabetic or definitely not diabetic by above approach will be eligible for the study. Those indeterminant may be used for keratoplasty, but not eligible for the study.

Diabetes Risk Categorization

Once diabetes status determination is complete, if found to have diabetes, additional information will be obtained to determine diabetes risk categorization on a 1 to 5 scale.

Specifically, the following aspects will be determined to calculate the diabetes risk categorization score:

- Any history of diabetes mellitus [1 point]
- Body mass index $> 30\text{kg}/\text{m}^2$ [1 point]
- Hypertension [1 point]

Additionally, 2 points are added to the score for any of the following, regardless of how many are chosen:

- Diabetes mellitus history of at least 10 years
- Insulin dependent outpatient

- Possible comorbidities
 - peripheral nerve damage/neuropathy
 - renal failure and/or dialysis, chronic kidney disease
 - stroke
 - myocardial infarction
 - leg ulcers or amputations
 - peripheral vascular disease
 - diabetic retinopathy with proliferative disease including vitreous hemorrhage
 - diabetic retinopathy with history of retinal laser
 - diabetic retinopathy with history of vitrectomy
 - diabetic retinopathy with history of intravitreal anti-VEGF therapy

Once diabetes status and severity are determined a computer program will be able to run a minimization procedure to select a donor cornea for a given participant DMEK surgery. For the first eye of each participant, if only one donor cornea is available, then this cornea is selected. Otherwise, if all available donor corneas are the same donor diabetes classification, then a cornea is randomly selected from all available. Otherwise, if at least one donor cornea is from each donor diabetes classification, a minimization procedure will select based on achieving balance on several factors, including the surgeon, and the donor diabetes risk categorization score.

For participants with two study eyes, if the first eye received a cornea from a known diabetic donor, then the second eye will receive a cornea from a donor the eye bank determined as non-diabetic, if available. If a cornea from a donor the eye bank determined as non-diabetic is not available, then surgery must be postponed or performed outside of the study. If the first eye received a cornea from a donor the eye bank determined as non-diabetic, then the minimization procedure will run and the second eye could receive a cornea from a known diabetic or nondiabetic donor.

The most important aspect of the protocol for the eye banks is maintaining masking of the surgeon and surgeon staff from any direct or indirect knowledge of the diabetic status of the donor tissue assigned to study participants.

The surgeon will be masked to all other donor parameters except storage solution. NO eye bank's standard reports and labels (including donor tissue report, donor cornea container label, recipient information form, package insert form and adverse reaction report) **can be sent to the surgeon**. Study-specific documentation will be used in lieu of these reports. See the Eye Bank Manual of Procedures for a summary of the EBAA waivers and other references, and examples of the DEKS Donor Tissue Label, DEKS Donor Tissue Report, DEKS Adverse Reaction Report, and DEKS Shipping Label.

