3.2.4 DMEK Lenticule Preparation

Detailed procedures are found in the DEKS Eye Bank Procedures Manual. Each DEKS eye bank will perform their DMEK lenticule preparation following their usual technique while documenting technique, and observations as to any problems during the stripping. Most importantly, each eye bank will ensure that the technician performing the prep will be masked as to the diabetes status of the donor.

For both the eye bank- and surgeon- prepared DMEK preps, the extent of endothelial cell damage post prep utilizing trypan blue will be assessed by the masked technician (or surgeon). The masked technician (or surgeon) will also perform an assessment of scroll tightness modified from earlier description whenever possible⁴⁸. Whether eye-bank or surgeon-prepared, the preferred time from DMEK donor preparation to surgery will be at the discretion of the surgeon, but tracked. Also, if corneal tissue is pre-loaded by the eye bank, the eye bank will follow its normal loading procedure according to their standard operating procedures. The loading system will be recorded (i.e., injector, storage container) and the preferred time from loading to surgery will be at the discretion of the surgeon and tracked.

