7.4 Confidentiality

For security and confidentiality purposes, both the donor and the human subject participants will be assigned identifiers that will be used instead of their names for study purposes. However, protected health information, such as name and social security number, will need to be shared with the specific eye bank processing the participant's donor tissue (eye banks require additional unique patient identifiers) as part of the EBAA standard requirements of transplant processing and notification; this information will be shared directly between the clinical site and their respective eye bank as per standard practices and therefore will not be stored in the study database. Alternatively, participant name and contact information will be shared by the sites through the study database and will be accessible (limited access) to members in the CWRU Coordinating Center for purposes of contacting participants that may be lost to follow-up. De-identified or coded participant information may also be provided to research sites involved in the study. The samples sent to the laboratories will be coded for HbA1c and AGE testing, and the labs will not receive any identifying information other than date of collection. Similarly, the images sent to CIARC will be coded and are not identifiable other than date of collection.

Chapter 8: Statistical Considerations

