8.5 Analysis Dataset and Sensitivity Analyses

The primary analysis will follow the intent-to-treat principle, with the following exceptions: it will exclude eyes that did not have DMEK surgery, received a non-study donor cornea tissue, had an anterior chamber IOL implanted during surgery, or experienced a suprachoroidal hemorrhage. It is highly unlikely that any of these events could be related to diabetes status of the donor.

Safety outcomes will be reported for all enrolled study eyes that have DMEK surgery, irrespective of whether the participant completed the study.

Sensitivity analyses for the primary and secondary outcomes, such as adjusting for significant operative complications and/or recipient diabetes, will be described in the SAP.

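### Section 3.2.2 allocates the donor group only when both donor classes are available; other eyes take their group from eye-bank stock or the second-eye rule, yet all are pooled as randomized with no record or analysis by route

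*Combined protocol and SAP*

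**What the plan says.** Section 3.2.2 gives three routes for a first eye.

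- One cornea: "For the first eye of each participant, if only one donor cornea is available, then this cornea is selected".
- Several corneas of one class: "if all available donor corneas are the same donor diabetes classification, then a cornea is randomly selected from all available". This draw picks a cornea but not a donor group.
- Both classes: "if at least one donor cornea is from each donor diabetes classification, a minimization procedure will select based on achieving balance on several factors".

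The second-eye rule is: "if the first eye received a cornea from a known diabetic donor, then the second eye will receive a cornea from a donor" whom the bank classed as non-diabetic. If there is no such cornea, the surgery is postponed or done outside the study.

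Section 2.1 explains that randomization is used as shorthand for minimization and sets a goal of 1420 randomized eyes. It does not say that some eyes never reach the minimization step.

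Section 8.5 begins: "The primary analysis will follow the intent-to-treat principle, with the following exceptions". The four exceptions are no DMEK, non-study tissue, an anterior chamber lens implanted at surgery, and suprachoroidal hemorrhage. None concerns the assignment route. The Section 8.6 model adjusts for corneal diagnosis and has a participant frailty; it has no route, eye-bank or surgeon term. Section 8.5 gives adjustment for operative complications and for recipient diabetes as examples of sensitivity analyses and leaves the detail to the SAP.

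**The concern.** The comparison of donor groups has the protection of an allocation procedure only where that procedure could have chosen either group. When one class is available, the group follows what the eye bank holds on that day. The comparison in those eyes is then sound only if stock is unrelated to the recipient's risk of failure.

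Nobody has to act improperly for this to fail. Section 8.3 itself describes regional differences: 24% diabetic donors at one source, 34% at another, and a third that reports 36% for 2015 and 27% for 2016–2017. If case mix, surgical technique or failure rate also differs by bank, region or calendar time, availability links donor group to failure risk. Section 3.2.2 names surgeon as a balancing factor, but balancing operates only in eyes that reach minimization.

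At stake is whether the report can say how many eyes were truly allocated and whether the result holds in them. Neither can be shown unless the route is recorded at the time, and it may not be possible to reconstruct it later.

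**Working it through.** **The plan's own figures.** The protocol gives no number of un-allocated eyes. The figures needed here are 1278 evaluable eyes, 1420 enrolled and about 1092 participants. 1278 / (1 − 0.10) = 1420, and 1420 / 1.3 = 1092; both reproduce. With the pooled-variance formula that matches the 2:1 table cells checked, the stated inputs (4% v 9%, two-sided 5%, 90% power) give 371 + 742 = 1113. The 1278 is the table's cell for 5% v 10%. So 1278 eyes have 93.3% power at 4% v 9%. That does not affect this point, but it is the baseline for the power figures below.

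**Share of first eyes with no choice of class.** For k independent available corneas and diabetic share p, P(one class only) = p^k + (1 − p)^k. The values p = 0.24 and 0.36 are the extremes in Section 8.3. The value of k is an assumption.

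| k | p = 0.24 | p = 0.36 | First eyes, of 1092 |
|---|---|---|---|
| 1 | 100% | 100% | 1092 |
| 2 | 63.5% | 53.9% | about 590–690 |
| 3 | 45.3% | 30.9% | about 340–490 |
| 5 | 25.4% | 11.3% | about 120–280 |
| 8 | 11.1% | 2.8% | about 30–120 |

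Section 8.3 allows both corneas of one donor into the study. Mates share a class, so independence may understate these shares.

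**Second eyes fixed as non-diabetic.** On the protocol's assumptions, 0.30 × 1092 = 328 second eyes, of which 1/3, about 109, follow a diabetic-donor first eye.

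**Size of confounding by availability (illustration).** Take no true donor effect and two equal strata of eyes, with diabetic shares of 24% and 36%. The failure rates are assumed. For 3% and 5%:

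- diabetic group: (0.24 × 0.03 + 0.36 × 0.05) / 0.60 = 4.20%
- non-diabetic group: (0.76 × 0.03 + 0.64 × 0.05) / 1.40 = 3.91%
- spurious difference: 0.29 points

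With 426 v 852 eyes and an average failure rate of 4%, the standard error is √[0.04 × 0.96 × (1/426 + 1/852)] = 1.16 points. The two-sided type I error is then about 5.7%. The same steps for 3% v 8% give 0.71 points and 8.3%; for 2% v 10% they give 1.14 points and 12.8%. A wider gap in diabetic share would give more: 10% v 57%, with failure rates of 3% v 6%, gives 1.6 points. Nothing in the documents points to a gap of that size.

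**Power of a restricted analysis (4% v 9%, 2:1, starting from 1278 eyes).** Power = Φ[(0.05 − 1.96 × SE0) / SE1], where SE0 is the pooled and SE1 the unpooled standard error.

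- Two-thirds allocated, 284 v 568 eyes: (0.05 − 1.96 × 0.01680) / 0.01887 = 0.90, power 82%.
- Half allocated, 213 v 426 eyes: (0.05 − 1.96 × 0.01940) / 0.02179 = 0.55, power 71%.

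**The case against.** A reader might go further and infer a failure of allocation concealment. On donor status, "the eye bank will define the donor as having diabetes using ICD-10 codes and medical records". The only masking stated inside the bank is that "each eye bank will ensure that the technician performing the prep will be masked as to the diabetes status of the donor". Section 7.4 says participant information "will need to be shared with the specific eye bank processing" the tissue. Staff could then, in principle, set a recipient's group by listing or holding back a cornea. The documents do not support that inference. Sections 7.4 and 10.3.2 describe identifiers such as name and social security number. They mention no prognostic data and do not say that sharing comes before assignment. No section says who enters the corneas or that one may be withheld. Surgeon, site staff and participant are masked. Surgery is scheduled 5 to 90 days after enrollment while tissue is kept at most 11 days, so for most of that range the cornea cannot yet exist at enrollment. An illustration of such steering also stays small: high-risk recipients (assumed 15% v 4% failure) 5 points rarer in the diabetic group, with half the eyes un-allocated, gives 0.05 × 0.11 × 0.5 = 0.3 points, and towards no difference. Steering is possible, not shown.

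Three further objections carry weight.

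- **Lists may be long.** One source in Section 8.3 reports 10,672 donors in a year, about 320 per 11 days; another reports 4,260 over 2015–2018, about 32 per 11 days. This is before donor eligibility and competing demand, both unknown, so it does not settle the list size.
- **The rule is open and has a reason.** Every route is printed, and a class that is not in stock cannot be assigned. This justifies the rule, but not leaving the route unrecorded.
- **Safeguards may be written elsewhere.** The protocol defers to a SAP and to eye-bank manuals whose text is not in the combined document. The supportable statement is that the protocol specifies no analysis by route. Section 8.10 tabulates baseline characteristics by donor group, which would show measured imbalance but not by route.

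**Conclusion.** The point holds as a gap in recording and analysis. In two of the three first-eye routes, and for second eyes after a known-diabetic-donor first eye, no allocation step chooses the donor group. These eyes are pooled with minimized eyes, and the protocol states no way to separate them. It is not a demonstrated concealment failure.

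The share of first eyes affected could be more than half or only a few percent. That depends on the list size, which the documents do not give, and on the independence of corneas. With the documented range of donor shares and assumed differences in failure rate, the spurious difference is about 0.3 to 1.1 points against a design effect of 5. It is therefore unlikely to produce the design effect by itself, although at the upper end of those assumptions the type I error would exceed 5% by a margin worth knowing about. This is a cheap improvement that lets the trial show its result in the eyes that were truly allocated.

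**What to change.** **Section 3.2.2.** State that, at the time of assignment, the program stores (a) the eligible corneas entered as available, with their diabetes class, and (b) the eye's route: minimized with both classes available, one class only, one cornea only, or fixed by the second-eye rule. Where eye-bank routine permits, the list is fixed before the program is run for that participant.

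**Section 8.5.** Report eyes by route and donor group. Prespecify a sensitivity analysis that fits the primary model only to eyes whose group was chosen by minimization with both classes available. Leave out second eyes fixed as non-diabetic, even if both classes were on the list.

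**Cost.** Stored fields in the assignment program, a sentence in the eye-bank procedures and one extra analysis, with no added participants or tests. Fixing the list in advance may not suit every bank, because tissue suitability and timing depend partly on the surgeon's requirements; hence the qualifier. The restricted analysis has fewer eyes and a wider interval, with power falling to the 82% or 71% shown above. It should support the primary analysis, not replace it, and a non-significant result in that subset alone should not be read as contradicting it.
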